Bias: Any disparities in the data generated compared with the national population and the immunisation recommendations in the UK will be discussed.

Study size: As per EMA requirement and Vaccine Working Party (VWP) recommendations, a target of at least 1000 vaccinees across all age groups (6 months to 5 years; 6 to 12 years; 13 to 17 years; ≥18-65 years; >65 years). The sample size proposed in this study accounts for the probability of observing at least one event in the 10 enrolled GP practices together with the level of precision associated with the finding.

Statistical methods: Weekly and cumulative incidence rates of AEIs within 7 days following vaccination with a seasonal influenza vaccine (GSK's *Fluarix Tetra* or another influenza vaccine) will be estimated, with 95% confidence intervals (CIs).

Outputs:

Weekly analysis: A weekly analysis of influenza vaccination and uptake by vaccine brand, different age and at-risk (as per UK CMO recommendations) groups and reports of AEIs in vaccinees will be produced. Those reported at consultations in the practice (medically attended) as well as those reported through ADR cards will be listed.

Final analysis: Interim weekly safety reports and a final comprehensive study report at the end of observation period will be produced. The findings will be discussed in light of the rates of adverse reactions observed in the RCGP network, in clinical trials performed with GSK's seasonal influenza vaccines and, as appropriate, with rates observed in EPI-FLU-045 and EPI-FLU-046 studies.

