The Clinical Informatics Research Group, in the Department of Clinical and Experimental Medicine (DCEM) at the University of Surrey is home of the data and analysis hub for the Royal College of General Practitioners Research and Surveillance Centre (RCGP RSC). The RCGP RSC provides a national primary care surveillance system and is supported by Public Health England (PHE). The RCGP RSC network of GP practices has a membership designed to give national coverage of 1.5%-2% of the English population.ⁱⁱⁱ The data processing, analysis capability, and leadership of the RCGP RSC developed by and are performed at the University of Surrey will be used for this investigation.

The most important work of the RCGP RSC network is its influenza surveillance; many GP practices have been involved in this work for decades^{iv}. Data are uploaded from the network on a weekly basis to a secure sever with the possibility to switch the frequency of the release to a twice weekly upload during epidemics. The methods developed by the University of Surrey will be used in this passive enhanced safety surveillance study, with a focus on adverse events reporting after vaccination.

Seasonal influenza vaccines present several specific challenges for pharmacovigilance. These include immunisation in large population cohorts in a relatively short and fixed time period each year, and multiplicity of vaccine products on the market with the need to conduct product-specific safety surveillance.

Routine pharmacovigilance systems for influenza vaccines would need capability to rapidly detect and evaluate potential new safety concerns each influenza season. The main objective of enhanced safety surveillance is to detect and evaluate a potential increase in product and batch-specific reactogenicity and allergic events in a near real-time manner in the earliest vaccinated cohorts in order to react accordingly as promptly as possible.

Similarly to the first two pilot studies, the Enhanced Passive Surveillance approach is the one chosen for this third pilot study. The use of customised ADR cards is the enhancement provided over simple AEI surveillance through routine data collection.

The UK national flu immunisation programme 2017/18 – recommendations

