1. General Practice EHR data recorded by the practice team. Weekly data about vaccine exposure, and any subsequent AEIs will be uploaded (anonymised) to University of Surrey. The EHR data contains both AEIs recorded by the practice team, as well as data reported to the GP practice on an ADR card by a vaccinated patient.
2. ADR cards completed by patients. Among the 10 participating GP practices, patients who are vaccinated against influenza will be provided ADR cards. These ADR cards customised following practice feedback to match EMA requirements will be used to collect AEIs reported after the receipt of influenza vaccination.

The method and governance procedure has been developed by the University of Surrey, using an approved provider, Apollo. If not applicable, alternatively, another approved data extraction supplier will be chosen, or the relevant study data will be directly extracted by the University of Surrey team using standard data extraction tools such as Morbidity Information Query Export Syntax (MIQUEST), tool sponsored by the Department of Health.

Data extractions will be conducted in accordance with the Research Group's standard operating procedures in data extraction, pseudonymisation, and transfer.

Pseudonymisation is a process that involves the removal of all personal identifiers – such as name, date of birth, etc. Furthermore, encrypted data will be kept during transfer and on a secure network that meets NHS Information Governance standards to minimise the risk of re-identification. Pseudonymisation is the standard approach for this type of surveillance. A legally binding definition of pseudonymisation has been introduced into European law^x on the recommendation of the European Data Protection Supervisor (EDPS)^{xi}.

Data are anonymised (strictly defined as “pseudonymised”) as near to source as possible. All data are strongly encrypted by a combination of symmetric and asymmetric encryption algorithms: Triple DES¹ and RSA 1024² before transmission, and utilises public and private key pairs unique to each project. Pseudonymisation is applied at this stage to allow for backwards identification should there be a need to do so as part of an ethically approved study.

For this study, it is required to link an adverse event to the vaccine (specific brand and batch number) administered. Pseudonymisation allows this without knowing any of the strong personal identifiers of that individual.

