3.3.2. Adverse Drug Reaction card

In order to facilitate the coding of data using a standardised approach, the 10 enrolled GP practices will also distribute an ADR card to their subjects receiving seasonal influenza vaccine or, as appropriate, to their parent or carer.

Subjects will be instructed to record adverse events (refer to [Annex 3](#)) within 7 days following vaccination and to return the card to their GP practice not later than 14 days post-vaccination. Data recorded on these cards will then be recorded by the GP staff into the subject's EHR. The coding will follow a standardised approach to data recording (refer to [Annex 2](#)) and will include a specific code to indicate that the information is derived from those cards.

Of note, the intent will be to issue cards to all vaccinated patients belonging to the enrolled GP practices, however, considering the UK influenza vaccination plan, some vaccinations are expected to occur outside of the GP settings. These are described as opportunistic vaccination, performed by third parties including pharmacists and thus it cannot be excluded that for some patients, ADR cards will not be distributed. These vaccinations will still be encoded in the EHR and those subjects will be included in the study. The adverse events (AEs) will be captured through the routine data collection process (refer to Section 3.3.1).

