5.3. Tertiary endpoints

- Seasonal influenza vaccination status among the subjects registered in the enrolled GP practices, overall, by vaccine brand, by age strata (6 months to 5 years; 6 to 12 years; 13 to 17 years; \geq 18-65 years; $>$ 65 years) and UK CMO-specified risk groups and date of vaccine administration collected in the EHR system
- Level of missing data related to vaccination information (date of event, vaccine brand, vaccine batch)
- Lag time between date of vaccine administration and date at which vaccination record is encoded in the EHR system
- Return of ADR cards
- Time interval between AEI onset date and recording in the EHR by source (medically attended vs via ADR cards)
- Time interval between the date data extraction and date at which the weekly report is generated

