In addition, weekly and cumulative incidence rates of any AEIs, each AEIs category (i.e. fever/pyrexia, local symptoms, any general non-specific symptom, any respiratory, any gastrointestinal, any sensitivity/anaphylaxis, rash, any musculoskeletal and any neurological AEs) and SAEs within 7 days post-vaccination period reported via ADR card will also be generated by Age group (6 months to 5 years; 6 to 12 years; 13 to 17 years; 18-65 years; >65 years) and by UK CMO-specified risk status (at risk, not at risk).

95% confidence interval (CI) adjusted for clustering effect of GP practices will be computed on all estimated incidence rates (Clopper-Pearson exact CI modified for cluster data as described in [Annex 1](#)).

The design effects and the intra-cluster correlation coefficients will also be estimated as described in [Annex 1](#) for the estimated cumulative incidence rates of AEIs reported on the ADR card within the 7 days post-vaccination period for the Cumulative vaccinated cohort Weeks 35-48 restricted to subjects who received the ADR card.

7.3.3. **Analyses of secondary objectives**

All analyses described for the primary objectives (refer to Section [7.3.2](#)) will also be generated by Vaccine group for all subjects included in the Weekly vaccinated cohorts and the Cumulative vaccinated cohorts (i.e. whether or not they received the ADR card).

For the weekly incidence rates (per 100 subjects):

- The denominator will be the number of subjects in the Weekly vaccinated cohort for the week of interest
- The numerator will be the number of subjects from the denominator who reported the specified AEI within 7 days following vaccination with the seasonal influenza vaccine using data entered in the EHR (i.e. AEIs derived from ADR card and medically attended AEIs)

For the cumulative incidence rates (per 100 subjects):

- The denominator will be the number of subjects in the Cumulative vaccinated cohort up to the week of interest
- The numerator will be the number of subjects from the denominator who reported the specified AEI within 7 days following vaccination with the seasonal influenza vaccine using data entered in the EHR (i.e. AEIs derived from ADR card and medically attended AEIs)

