7.3.7. Analysis on the RCGP RSC network of practices

The Royal College of General Practitioners Research and Surveillance Centre (RCGP RSC) network of practices includes approximately 170 GP practices.

The RCGP RSC network will be used to observe the trend of AEI rates using a larger sample of GPs.

The 2017 RSCGP RSC vaccinated cohort will include all subjects from the RSCGP RSC population

- who have not opted-out of data sharing
- who will be vaccinated against influenza at any point during the study vaccination period
- who have a valid NHS number recorded in EHR
- with date of birth recorded in EHR
- with gender recorded in EHR
- who are registered in EHR during the 7 days post vaccination period

The cumulative incidence rate (per 100 subjects) of each AEI within the 7 days post-vaccination period, with 95%CI, will be estimated by Vaccine group as follows:

- The denominator will be the number of subjects from the 2017 RCGP RSC vaccinated cohort
- The numerator will be the number of subjects from the denominator who reported the specified AEI during the 7 days following vaccination with the seasonal influenza vaccine using data entered in the EHR

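### In the text available, every AEI rate planned for the 10 practices includes card reports, so none is like-for-like with the RCGP RSC network rate in SAP 7.3.7

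*SAP*

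**What the plan says.** **Network rate.** SAP 7.3.7 takes as its numerator the subjects "who reported the specified AEI during the 7 days following vaccination with the seasonal influenza vaccine using data entered in the EHR". It gives the purpose as follows: "The RCGP RSC network will be used to observe the trend of AEI rates using a larger sample of GPs". The output is one cumulative rate for each AEI, by Vaccine group, in the 2017 network cohort.

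**Use of the network rate.** The protocol synopsis, under Final analysis, states: "The findings will be discussed in light of the rates of adverse reactions observed in the RCGP network". The same sentence also names GSK's clinical trials and, as appropriate, EPI-FLU-045 and EPI-FLU-046.

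**Study rate with the same label.** For the 10 practices, SAP 7.3.3 counts AEIs "using data entered in the EHR (i.e. AEIs derived from ADR card and medically attended AEIs". This wording matches 7.3.7, but here it is spelled out as two sources combined.

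**Where the cards are.** Protocol section 5a states: "Among the 10 participating GP practices, patients who are vaccinated against influenza will be provided ADR cards". Protocol section 4a adds: "The use of customised ADR cards is the enhancement provided over simple AEI surveillance through routine data collection". No passage describes cards in other network practices.

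**Identifying card data.** SAP 3.3.2 says the coding of card data "will include a specific code to indicate that the information is derived from those cards".

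**The concern.** One phrase, data entered in the EHR, appears to cover two kinds of ascertainment. In the study practices it takes in symptoms that patients were asked to tick on a card, together with AEIs recorded by the practice. In the network it seems to take in only what the practice recorded.

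The study exists to notice an increase in AEI frequency. Of the comparators named in the synopsis, the network is the only one from the same season. A reader who sets a study rate beside the network rate cannot tell a real excess from the effect of handing out cards. Equally, a study rate close to the network rate would not show that frequency was normal, because the two numerators were collected differently.

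**Working it through.** **Step 1. Which AEI rates are planned for the 10 practices?**

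| Place | Numerator source | Denominator |
|---|---|---|
| SAP 7.3.2 | card only | vaccinees who received a card |
| SAP 7.3.3 | card plus medically attended | all vaccinees |
| SAP 7.3.6.1 | card only; and card plus medically attended (unclustered CI) | card returners; all vaccinees |
| SAP 7.3.6.2 | card only | card returners |
| SAP 9.1.1 (weekly reports) | all EHR data, which contain entered cards (Protocol 5a) | vaccinees of the week |
| SAP 7.3.7 (network) | EHR data, no card source named | network vaccinees |

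No row for the study practices leaves out card-reported AEIs. Medically attended AEIs are separated in two other places, and neither gives an incidence rate. One is a weekly listing in the protocol synopsis. The other is the SAP 5.3 timeliness endpoint: "Time interval between AEI onset date and recording in the EHR by source (medically attended vs via ADR cards".

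**Step 2. How large could the gap be?** The plan gives no figure, so this is an illustration.

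- c = share of vaccinees given a card: 0.90 (assumed)
- r = card return: 0.50 (Protocol 4a reports approximately 50% in EPI-FLU-046)
- q = AEI risk reported by returners: 5%, 10%, 20% (assumed)
- m = medically attended AEI risk: 1%, 2%, 5% (assumed, the same in both settings)

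The routine-only rate is m. The pooled study rate P depends on how the two sources overlap:

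- Independent reports: P = c[1 − (1 − rq)(1 − m)] + (1 − c)m
- Full overlap (the smaller group lies wholly within the larger): P = c·max(rq, m) + (1 − c)m

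Central case, q = 10% and m = 2%:

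- Independent: 0.9 × [1 − 0.95 × 0.98] + 0.1 × 0.02 = 0.9 × 0.069 + 0.002 = 0.0641. Ratio 0.0641/0.02 = 3.2.
- Full overlap: 0.9 × 0.05 + 0.1 × 0.02 = 0.047. Ratio 0.047/0.02 = 2.35.

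Extremes:

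- Lowest, q = 5%, m = 5%, full overlap: 0.9 × 0.05 + 0.1 × 0.05 = 0.05. Ratio 1.0. (Under independence it is 0.071375/0.05 = 1.4.)
- Highest, q = 20%, m = 1%, independent: 0.9 × 0.109 + 0.1 × 0.01 = 0.0991. Ratio 9.9.

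**Step 3. What if the 10 practices are in the network?** Assume all 10 are among the approximately 170 network practices and all are of equal size. In the central case under independence the network rate becomes (10 × 0.0641 + 160 × 0.02)/170 = 0.0226. The ratio is 0.0641/0.0226 = 2.8. Membership would narrow the gap without closing it.

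**Step 4. Precision of a medically attended rate.** Protocol Table 1 at 5,000 vaccinees and 1% prints 0.7–1.3% with RSE 14.1%. Clopper-Pearson gives 0.74–1.32%, and √(0.99/50) = 14.1%, so the table reproduces. At 2% the exact interval is 1.63–2.43% (printed 1.6–2.4%). For a rare single AEI at 0.10%, RSE = √(0.999/5) = 44.7%, as printed. None of these allows for clustering.

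**The case against.** **The network is there for trend, and everything is descriptive.** SAP 7.3.7 mentions trend and SAP 8 says all analyses are descriptive, with no formal comparison planned. That limits the damage to interpretation. But 7.3.7 produces a single cumulative level, and descriptive rates read side by side still need the same kind of numerator.

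**Medically attended AEIs are already reported.** The synopsis promises a weekly listing of them. A listing is not a rate, and SAP 9.1.1 defines only an all-EHR rate.

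**Other comparators exist.** This stands. EPI-FLU-046 used customised cards, so a card-based reference is available. A reader might infer that the study has nothing against which to judge unusual frequency. The documents do not support that: the gap concerns the same-season network level only.

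**Cards need not inflate the rate.** This also stands. A reader might infer that card solicitation must push the study rate above the network rate. If card reporters largely consult as well, the ratio can be 1.0.

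**Source may not be separable for each event.** This partly stands. The primary analysis already needs card-reported AEIs to be identified, and SAP 5.3 speaks of source. SAP 7.3.4, however, implements timeliness by card-returned status, which describes the subject and not the event.

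**Brand comparisons.** A reader might also infer that the pooled rates in 7.3.3 are confounded between vaccine brands. That would require card receipt to differ by brand, which the documents do not show. The primary rates are in any case restricted to card recipients.

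**Conclusion.** The point holds within limits. On the text available, no AEI rate planned for the 10 practices rests on routine recording alone, so none matches the network rate in SAP 7.3.7, although the protocol undertakes to discuss the findings in light of network rates.

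The conclusion rests on two things that cannot be settled from the documents. First, that network practices issue no cards is an inference from where cards are described. Second, the TFL annex is not available and could contain a matching table.

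The size is unknown. The range of 1.0 to 9.9, and the central 2.35 to 3.2, follow from assumed inputs and assume equal true risk and equal consultation in both settings. They show that the gap may be absent or large, and that the planned outputs would not tell a reader which. The primary card-based rates and the weekly surveillance are not affected.

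**What to change.** In the final analysis, add to SAP 7.3.7:

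- Cumulative Weeks 35–48 medically attended AEI rates for all vaccinees in the 10 practices, for each AEI and by Vaccine group, set beside the network rates. Add an any-AEI row for both cohorts.
- A rule for dual reporting: count an AEI recorded at a consultation within 7 days even if it is also on a card, and exclude only AEIs whose sole source is the card.
- A statement of whether network practices use cards.
- A statement of whether the 10 practices are in the network cohort. If they are, report the network rate without them or without card-only AEIs.

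The pooled rates in 7.3.3 and the weekly reports stay as they are.

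**Cost.** One further table of about 30 AEIs by four Vaccine groups. Intervals for rare single AEIs will be wide (RSE 44.7% at 0.10% and 5,000 vaccinees), wider still by Vaccine group. Comparability improves but stays imperfect, because SAP 3.3.1 asks the study practices to use a preferred code list. Before committing, confirm that the card code links to individual AEI records, and that an AEI both consulted for and reported on a card can be recognised as such.

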8. ANALYSIS INTERPRETATION

All analyses are descriptive.

9. CONDUCT OF ANALYSES

9.1. Sequence of analyses

Interim weekly safety reports and a final analysis after study end will be done.

Description	Analysis ID	Disclosure Purpose	Dry run review needed (Y/N)	Study Headline Summary (SHS) requiring expedited communication to upper management (Yes/No)	Reference for TFL
Final analysis after study end	E1_01	Study report, CTRS	No	Yes	Refer to EPI-FLU-055 VS UK (207781) TFL .docx
Interim analyses	E1_02	Safety monitoring	No	No	Weekly safety reports of EPI-FLU-046

9.1.1. Interim analyses

Weekly safety reports of influenza vaccination and uptake by different age and risk groups and the EMA listed AEIs reported by the vaccinated subjects will be generated during the study period. These analyses will be performed overall and by vaccine brand (*Fluarix Tetra* vs. others).

The weekly incidence rates of each AEI within 7 days will be estimated as follows:

- The denominator will be the number of subjects vaccinated with a seasonal influenza vaccine during the week of interest
- The numerator will be the number of subjects from the denominator reporting the AEI within 7 days following vaccination with a seasonal influenza vaccine using data entered in the EHR

A safety report will be generated for each ISO week 35 to 48.

The safety report of a specific ISO week will be provided 3 weeks after that week to allow for data to be encoded in EHR.

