10	50000	5%	1785	17	1.00%	0.6%	1.5%	>99.99%	23.6%
11	50000	5%	1964	19	1.00%	0.6%	1.5%	>99.99%	22.5%
12	50000	5%	2142	21	1.00%	0.6%	1.5%	>99.99%	21.5%
13	50000	5%	2321	23	1.00%	0.6%	1.5%	>99.99%	20.7%
14	50000	5%	2500	25	1.00%	0.6%	1.5%	>99.99%	19.9%
1	50000	2%	71	0	1.00%	0.0%	5.1%	51.01%	118.1%
2	50000	2%	142	1	1.00%	0.0%	3.9%	76.00%	83.5%
3	50000	2%	214	2	1.00%	0.1%	3.3%	88.36%	68.0%
4	50000	2%	285	2	1.00%	0.1%	2.5%	94.30%	58.9%
5	50000	2%	357	3	1.00%	0.2%	2.4%	97.23%	52.7%
6	50000	2%	428	4	1.00%	0.3%	2.4%	98.65%	48.1%
7	50000	2%	500	5	1.00%	0.3%	2.3%	99.34%	44.5%
8	50000	2%	571	5	1.00%	0.3%	2.0%	99.68%	41.6%
9	50000	2%	642	6	1.00%	0.3%	2.0%	99.84%	39.3%

Week	Expected Population medically followed by the enrolled practices	Cumulative Vaccine coverage after 14 weeks	Cumulative number of Vaccinated subjects	Cumulative number of Subjects reported ≥ 1 AEI	Average Proportion of AEI reported	Lower 95%CL	Upper 95%CL	Cumulative Probability to observe at least one event	Associated Relative standard error (RSE)
10	50000	2%	714	7	1.00%	0.4%	2.0%	99.92%	37.2%
11	50000	2%	785	7	1.00%	0.4%	1.8%	99.96%	35.5%
12	50000	2%	857	8	1.00%	0.4%	1.8%	99.98%	34.0%
13	50000	2%	928	9	1.00%	0.4%	1.8%	99.99%	32.7%
14	50000	2%	1000	10	1.00%	0.5%	1.8%	>99.99%	31.5%

Statistical analyses

All data processing and statistical analysis will be performed within the secure IT environment of the Clinical Informatics Research Group, at the University of Surrey. R and SAS Software will be used for the statistical analyses. Statistical analyses will be described in details in a statistical analysis plan, including the methodology to account for the clustering effect.

Coded data will be interpreted by the creation of ontologies allowing to map to case-definitions, where available. However, no in depth descriptions required for case definition will be used such as in clinical trials. Meaning will be inferred from brief clinical coded information.

Sequence of analysis

Interim analysis

Weekly safety report

Weekly safety reports will be generated in order to be able to detect and potentially report any safety concerns in near real time manner. Analyses will be performed overall and by vaccine brand (*Fluarix Tetra* vs. others).

The weekly incidence rates of AEIs within 7 days will be estimated as follows:

- The denominator will consist of the number of subjects vaccinated two weeks before the week of interest

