1. INTRODUCTION

The complete statistical analysis plan and results presentation is divided into 2 parts: the first part detailing the analyses to be performed (known as SAP, current document) and a second part, annex (called TFL) describing the flow and format of tables, figures and listings to be annexed to the Study Report.

This SAP describes the final analysis to be performed after the end of the observation period on all data pertaining to the above study.

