3. STUDY DESIGN

3.1. Study design overview

- Type of design: prospective post-authorisation passive enhanced safety surveillance study in the United Kingdom (UK).
- Co-Sponsors: GSK and the University of Surrey, Guildford UK.
- Study vaccination period: intended to be from 01SEP2017 (start of the seasonal influenza vaccination) up to 30NOV2017.
- Study period: intended to be from 01SEP2017 (start of the seasonal influenza vaccination) up to 7 days after last study participant vaccinated.
- Study General Practitioner (GP) practices: 10 GP practices ordering mainly GSK's Fluarix Tetra vaccine for the 2017/18 season will be enrolled in the study before the start of the seasonal influenza immunisation season. These 10 GP practices will be selected based on their willingness to participate, their location (distributed across England (in London, a Northern city, and rural settings in the North and South)) and that the participating population spans different age strata, different levels of deprivation, different ethnic mix, different brand of computerised medical record systems, and different practice sizes. GP practices will also be included based on their ability to comply with the study protocol requirements.
- Study participants: subjects who receive influenza vaccination between 01SEP2017 and 30NOV2017 in the 10 enrolled GP practices and who have not opted-out of data sharing.
- Number of subjects: according to the sample size assumption (conservative approach), it was estimated to be able to reach a number of 50,000 subjects registered in the 10 enrolled GP practices with an estimate of 5,000 vaccinated subjects with 7 days of follow-up after vaccination.
- **Type of study:** self-contained.

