3.4. Data extract from EHR

The following data from subjects in the 10 enrolled GP practices will be imported (anonymised) into the secure servers of the University of Surrey:

- Demographic information: age, gender, ethnicity, date of registration
- Seasonal influenza vaccine information: date of administration, brand and batch number when available
- Postcode: to understand any inequities in access according to level of social deprivation using Geographical Information System (GIS) methods. Full postcodes will be immediately transformed into deprivation scores, using the Index of Multiple Deprivation (IMD), within GP computer systems upon extraction
- Primary care consultations following vaccination, any other markers of health care utilisation, and referral to further care.
- Pre-specified European Medicines Agency (EMA) adverse events of interest (AEIs) ([Annex 2](#)) or any other reported AE recorded in the EHR. Only coded data (Read code and CTV3), i.e. where the GP codes a disease or symptom into the EHR system, will be extracted
- Data from at least one year prior to the start of the study to determine the category of UK Chief Medical Officer (CMO)-specified risk group for influenza vaccination the subjects belong to:
 - Life-style/risk factors – e.g. body mass index, smoking status
 - Records of other diseases and long term conditions – e.g. chronic respiratory disease, chronic heart disease, chronic kidney disease, chronic liver disease, chronic neurological disease, diabetes, immunosuppression, pneumonia, etc
- Pregnancy status during the course of the study period

No individual patient level data will be released to GSK.

GSK will be blind to GP practice identities, and the locality at which any AE occurs.

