3.5. Summary of different groups

The following groups will be used for the statistical analyses.

Vaccine groups for vaccinated subjects:

Group name	Group order in tables	Group label in tables
Vaccine	1	Vaccinated (GSK's Fluarix Tetra)
	2	Vaccinated (Non-GSK)
	3	Vaccinated (Unknown)
	4	Vaccinated (All)

Age groups (categories recommended by EMA):

Group name	Group order in tables	Group label in tables
Age	1	6 months to 5 years
	2	6-12 years
	3	13-17 years
	4	18-65 years
	5	>65 years

UK CMO-specified risk groups*; note that subjects may be assigned in more than one specified risk group:

Group name	Group order in tables	Group label in tables
UK CMO-specified risk groups	1	Any risk group
	2	Asthma
	3	Chronic Respiratory Disease
	4	Chronic Heart Disease
	5	Chronic Kidney Disease
	6	Chronic Liver Disease
	7	Diabetes
	8	Immunosuppression (includes relevant cancer treatment)
	9	Chronic Neurological Disease
	10	Asplenia
	11	Carer
	12	Pregnancy
	13	2 to 8 years old
	14	65 years old and over
	15	Not at risk

* Some high risk groups e.g. in residential care are not well recorded in GP data

UK CMO-specified risk status:

Group name	Group order in tables	Group label in tables
UK CMO-specified risk status	1	At risk
	2	Not at risk

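### The SAP has no rule for recovering a missing vaccine brand from the recorded batch number, so Fluarix Tetra recipients with a batch but no brand drop out of the Fluarix Tetra rates

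*SAP*

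**What the plan says.** **Brand groups.** SAP 3.5 opens with "The following groups will be used for the statistical analyses" and lists four vaccine groups: Fluarix Tetra, Non-GSK, a third for unknown brand (labelled "Vaccinated (Unknown"), and all vaccinated. SAP 7.3 presents the safety analyses by these groups.

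**Data available.** SAP 3.4 extracts "date of administration, brand and batch number when available". The protocol (Research methods, Data extraction and data management) says the study must be able to link an adverse event to the specific brand and batch given. The protocol's introduction describes the aim of enhanced surveillance as near real-time detection of product- and batch-specific reactogenicity.

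**Missing brand is foreseen.** It is a tertiary endpoint (SAP 5.3), but no expected percentage is given.

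**Use of batch number.** SAP 7.2 tabulates batch for subjects already classed as Fluarix Tetra and lists Fluarix Tetra batches by region and week. SAP 7.3.4 counts how often batch is recorded. SAP 12.2.3 contains only the rule that the first vaccination counts. No other part of 12.2 mentions brand or batch.

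**Weekly reports.** SAP 9.1.1 says "These analyses will be performed overall and by vaccine brand" and names two categories, Fluarix Tetra and others. The protocol's weekly-report text uses the same two. Neither says where a record without a brand goes, and 9.1.1 does not refer to 3.5.

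**The concern.** The practices are "10 GP practices ordering mainly GSK's Fluarix Tetra vaccine for the 2017/18 season". A vaccination given from practice stock with no brand recorded is therefore more likely than not to be Fluarix Tetra. Where its batch number is on file, the brand can often be worked out, yet the plan has no step that does so.

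Three things follow for such a record. Its subject is missing from the Fluarix Tetra denominator. Any adverse event of interest it carries is shown under Unknown rather than under the brand of interest. It also drops out of the batch table in SAP 7.2, which is limited to recipients already classed as Fluarix Tetra. For a study that must report on one product and trace events to batch, usable exposure data are left unused.

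**Working it through.** **1. Reproduce the plan's own figure.** Protocol Table 1, 5,000 vaccinees, 1% event probability. Relative standard error (RSE) = √((1−p)/(np)) = √(0.99/50) = 14.1%, as tabulated. The exact 95% interval is 0.74% to 1.32%, against 0.7% to 1.3% in the table. The same RSE formula is used below.

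**2. Inputs.**
- Vaccinees N = 5,000 (SAP 3.1).
- Fluarix Tetra share f: the documents say only that practices mainly order it. Assumed 80%, range 60% to 90%.
- Proportion with brand missing u: not given. Assumed 5% to 20%, independent of brand and of having an event.
- Event rate in Fluarix Tetra recipients: assumed 2%.
- Clustering by practice is ignored.

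**3. Loss from the Fluarix Tetra group.** Subjects kept = N·f·(1−u).

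| f | u | Fluarix Tetra subjects kept | RSE of the rate |
|---|---|---|---|
| 80% | 0 (full recovery) | 4,000 | √(0.98/80) = 11.1% |
| 80% | 5% | 3,800 | √(0.98/76) = 11.4% |
| 80% | 10% | 3,600 | √(0.98/72) = 11.7% |
| 80% | 20% | 3,200 | √(0.98/64) = 12.4% |
| 60% | 0 → 10% | 3,000 → 2,700 | 12.8% → 13.5% |
| 90% | 0 → 10% | 4,500 → 4,050 | 10.4% → 11.0% |

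Recovery may be partial. If half of the missing brands at f = 80%, u = 10% have a usable batch, 200 subjects return, giving 3,800 and an RSE of 11.4%.

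Under these assumptions the Fluarix Tetra rate is not biased. At u = 10%, though, on average one in ten events in Fluarix Tetra recipients is displayed under Unknown. That matters most for rare events, where the count may be one or two.

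**4. Weekly reports, only if Unknown were merged into the other brands.** The Fluarix Tetra share of the merged group is c = f·u / ((1−f) + f·u). If the true ratio is 2, the merged group's rate is (1+c) times the rate for the true other brands, so the displayed ratio is 2/(1+c).
- f = 80%, u = 5%: c = 0.04/0.24 = 0.167, displayed ratio 1.71.
- f = 80%, u = 10%: c = 0.08/0.28 = 0.286, displayed ratio 1.56.
- Range: 1.87 (f = 60%, u = 5%) down to 1.22 (f = 90%, u = 20%).

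If Unknown is kept separate, the expected ratio stays 2.00 and only the loss in step 3 applies.

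**The case against.** **The weekly contrast.** A reader might infer from the two-way wording in SAP 9.1.1 that unknown brands fall among the other brands and that the in-season contrast is diluted. One can argue for this: 9.1.1 does not cite 3.5, the SAP's introduction says "This SAP describes the final analysis to be performed after the end of the observation period", and the weekly table template is the previous season's reports. The documents do not support it as fact. The same two-way phrase defines the primary and secondary objectives and endpoints (SAP 4.1, 4.2, 5.1, 5.2), and the SAP carries those out with the four groups of 3.5, Unknown included. The previous season's template is not supplied, so its layout cannot be checked. Merging is one possible reading and no more.

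**Timing.** The SAP is dated 11 December 2017 and weekly reports are due three weeks after each ISO week. Week 46 ended on 19 November, so its report was due on 10 December. A change to 9.1.1 could reach only the reports for weeks 47 and 48. This objection stands for the weekly sentence. It does not touch the batch rule, which serves the final analysis.

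**Yield.** Batch, like brand, is extracted only when available, and the two may be missing together. Unknown brands may also come largely from pharmacies, where the practices' ordering pattern says little. Both points stand and limit the gain. The pharmacy point applies mainly to the secondary analysis, because the primary analysis is restricted to subjects who received a card and the practices hand out the cards.

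**Small harm.** The analyses are descriptive, no brand test is planned, and the precision loss is slight. This is fair. It makes the point modest but does not justify leaving collected exposure data unused.

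**Source of the look-up.** No passage says the sponsor gives the University a batch list. The look-up need not depend on one, because study records holding both brand and batch can supply it.

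**Conclusion.** The omission holds on either reading of the weekly wording. The SAP has no batch-to-brand step, so Fluarix Tetra recipients with a batch but no brand are left out of the brand group of interest, and the linkage the protocol asks for is not made for them.

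The size is modest. At an assumed 80% share, 10% missing and a 2% event rate, it is the difference between an RSE of 11.7% and 11.1% if recovery is full, and less if batch is also missing. The share, the proportion missing and the independence of missingness are all assumptions.

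Dilution of the weekly brand contrast is not established. The ratios of 1.71 and 1.56 show what merging would do under the stated assumptions. They do not describe what the plan does. On the weekly reports, the documents support only a request for clarification.

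**What to change.** **SAP 12.2.3.** Add: where brand is missing and a batch number is recorded, assign brand by matching to a look-up built from study records that hold both brand and batch, plus the sponsor's own Fluarix Tetra batch numbers if supplied to the University. Leave a record Unknown if its batch is unmatched or appears under more than one brand. Report the number reclassified, by vaccine group.

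**SAP 9.1.1.** Add one sentence stating that the 3.5 groups apply to the weekly reports, so Unknown is shown separately and not merged with the other brands. For reports already issued, the final report should say how unknown brands were handled.

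**SAP 7.3.4.** Add brand to the completeness items. The protocol's completeness analysis includes it, but the SAP lists only date and batch number.

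**Cost.** A look-up table built inside the University's environment, a sentence or two in each section and a count in one table. No new data collection is needed. The downsides are an occasional mistyped batch number causing a wrong or failed match, and only partial recovery where batch is missing too.
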